5.6 Total Expected Duration of the Clinical Trial

[Redacted]

5.7 Expected Duration of Each Subject’s Participation

[Redacted]

[Redacted]

**PROTOCOL ABT-CIP-10398 XIENCE 28 Global Study****5.8 Number of Subjects Required to be Included in the Clinical Trial**

[REDACTED]

5.9 Estimated Time Needed to Register this Number

[REDACTED]

5.10 Trial Completion

A Trial Completion eCRF must be completed when:

- the subject is considered lost to follow-up per the above definition or
- the subject withdraws from the clinical trial or
- the investigator withdraws the subject from the clinical trial or
- the subject has died or
- upon clinical trial completion or
- sponsor termination of trial.

Sponsor must be notified of the reason for subject discontinuation. The site will provide this information on the eCRF. Investigators must also report this to their EC as defined by their institution's procedure. Subjects will not be replaced.

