**PROTOCOL ABT-CIP-10398 XIENCE 28 Global Study**

Point of Registration
	
Subject registration will occur after the index procedure but prior to discharge and up to 3 days post index procedure, upon confirmation of the following:
 
 • Signed informed consent has been obtained; • Subject has met all the inclusion and none of the exclusion criteria (including both general and angiographic criteria).

Subject Follow-Up
	
Subjects registered in the trial will receive the following clinical follow-up:
 
 • 1 month (28-35 days): office visit (Note: for subjects who have difficulty scheduling an office visit due to special circumstances, 1-month follow-up may be performed via telephone per physician's discretion) • 3 months (90 ± 7 days): office visit/telephone contact (office visit is strongly recommended whenever possible) • 6 months (180 ± 14 days): office visit/telephone contact (office visit is strongly recommended whenever possible) • 12 months (365 ± 28 days): office visit/telephone contact (office visit is strongly recommended whenever possible)

Primary Analysis Sample Size Justification
	
To further evaluate the safety of 1-month DAPT, non-inferiority (NI) will be tested comparing 1-month DAPT to XIENCE V USA historical control for the primary endpoint of NACE from 1- to 6-month follow-up in a "1-month clear" population (defined as subjects who are free from myocardial infarction [modified ARC], repeat coronary revascularization, stroke, or stent thrombosis [ARC definite/probable] within 1 month (prior to 1-month visit but at least 28 days) after stenting AND have been compliant with 1-month DAPT without interruption of either aspirin and/or P2Y12 receptor inhibitor for > 7 consecutive days).
 
[REDACTED]
 
[REDACTED]
 
[REDACTED]
 
[REDACTED]
 
[REDACTED]
 
[REDACTED]
 
[REDACTED]
 
[REDACTED]
 
[REDACTED]
 
[REDACTED]
 
[REDACTED]

PROTOCOL ABT-CIP-10398 XIENCE 28 Global Study

	
 • [REDACTED]

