**PROTOCOL ABT-CIP-10398 XIENCE 28 Global Study****1.0 INTRODUCTION****1.1 Trial Design**

XIENCE 28 Global Study is a prospective, single arm, multi-center, open label trial to further evaluate the safety of 1-month (as short as 28 days) dual antiplatelet therapy (DAPT) in subjects at high risk of bleeding (HBR) undergoing percutaneous coronary intervention (PCI) with the approved XIENCE family of coronary drug-eluting stents.

The XIENCE family stent systems include commercially approved⁵ XIENCE Xpedition Everolimus Eluting Coronary Stent System (EECSS), XIENCE Alpine EECSS, XIENCE PRO^X EECSS⁶, XIENCE Pro^A EECSS⁷, or XIENCE Sierra EECSS which are all manufactured by Abbott Vascular, Inc, Santa Clara, USA. The above listed XIENCE stents will hereinafter be called “XIENCE” in this trial.

[REDACTED] Trial population consists of non-complex HBR subjects with up to three native coronary artery lesions (a maximum of two lesions per epicardial vessel) with reference vessel diameter between 2.25 mm and 4.25 mm. Eligibility of P2Y12 receptor inhibitor discontinuation will be assessed at 1-month follow-up. Subjects who are free from myocardial infarction (modified ARC), repeat coronary revascularization, stroke, or stent thrombosis (ARC definite/probable) within 1 month (prior to 1-month visit but at least 28 days) after stenting AND have been compliant with 1-month DAPT without interruption of either aspirin and/or P2Y12 receptor inhibitor for > 7 consecutive days are considered as “1-month clear”, and will discontinue P2Y12 receptor inhibitor as early as 28 days and continued with aspirin monotherapy through 12-month follow-up.

All registered subjects will be followed at 1, 3, 6 and 12 months post index procedure.

The data collected from the XIENCE 28 Global Study will be compared with the historical control of non-complex HBR subjects treated with standard DAPT duration of up to 12 months from the XIENCE V USA Study⁸, which is a US post-approval study to evaluate the safety of XIENCE V EECSS in “all-comer” population under real-world setting.

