- If a subject misses one or more non-consecutive follow-up contact time points it will be considered a missed visit. The subject may then return for subsequent visits. If the subject misses two consecutive time points and the above-mentioned attempts at communicating with the subject are unsuccessful, the subject will be considered lost-to-follow-up.

Note: Telephone contact with general practitioner, non-trial cardiologist or relative without presence of subject or indirect documentation obtained via discharge letters will not be considered as subject contact.

Missed Visits:

- If a subject misses one or more non-consecutive follow-up contact time points, the visit will be considered a missed visit and subject is not lost-to-follow-up.
- If subject responds via written communication (including email correspondence), providing the protocol required data, these data will be collected in the case report form and the visit will not be considered a missed visit.

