**PROTOCOL ABT-CIP-10398 XIENCE 28 Global Study**

Clinical follow-up visits should be conducted by the investigator or trial personnel who have been trained to the protocol. At 1-month follow-up visit, the investigator or designee will assess whether the subject is “1-month clear” and eligible for P2Y12 inhibitor discontinuation per criteria defined in **Section 6.3.2**.

All registered subjects will be followed up through 12 months, regardless of eligibility to discontinue P2Y12 inhibitor.

The following information will be collected at each of the time points:

- Any adverse events
- Use and compliance of protocol required antiplatelet medication
- Details of any subsequent coronary interventions (e.g., repeat PCI or CABG).

Note that information obtained through indirect contacts with a subject’s healthcare provider or immediate family member will NOT be considered as a trial visit.

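### Sections 5.5 and 5.10 close a subject as lost after two consecutive missed contacts and failed attempts, with no stated route back, although a scheduled contact that could still establish outcome status may lie ahead

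*Protocol*

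**What the plan says.** Protocol 1.1 sets the schedule: "All registered subjects will be followed at 1, 3, 6 and 12 months post index procedure". The Protocol Summary (Subject Follow-Up) gives the windows: "1 month (28-35 days): office visit", "3 months (90 ± 7 days): office visit/telephone contact", "6 months (180 ± 14 days): office visit/telephone contact", and a 12-month contact at 365 ± 28 days.

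Protocol 5.5 lists loss to follow-up among the possible reasons for discontinuation. The condition has two parts: "If the subject misses two consecutive time points and the above-mentioned attempts at communicating with the subject are unsuccessful". The attempts required at each time point are at least two calls on different days and, if these fail, a letter. The same section says that a subject may come back for later visits, but it says so for missed visits that are not consecutive.

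Protocol 5.10 then says "A Trial Completion eCRF must be completed when" one of six conditions holds. The first is that "the subject is considered lost to follow-up per the above definition"; the others are withdrawal by the subject, withdrawal by the investigator, death, trial completion and sponsor termination. The sponsor and the ethics committee must be told the reason for discontinuation.

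Protocol 6.4 states "All registered subjects will be followed up through 12 months, regardless of eligibility to discontinue P2Y12 inhibitor".

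The SAP imputes baseline characteristics for the propensity score (2.5) and adds a sensitivity analysis that imputes missing primary outcomes (2.9).

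**The concern.** The primary test (SAP 2.1.4) compares 1-6 month NACE rates, so each subject's status over that period matters. A late contact can still supply it. Under Protocol 7.3.1, serious events, cardiovascular events, strokes and bleeds are still collected after month 6, so a 12-month contact could reveal and date an event that happened before month 6. It could also settle vital status, and all-cause death is a NACE component. The sentence in 5.5 that retains deceased/alive status is worded for withdrawn subjects; nothing equivalent is stated for lost ones.

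If a site treats the completion form as the end of the matter, some recoverable outcomes become missing. Subjects who cannot be reached twice may be sicker than the rest. If they are, the trial-arm NACE rate is understated, which favours non-inferiority, the sole success criterion (SAP 1.6).

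**Working it through.** **1. When loss can be declared.** The inputs are the visit windows in the Protocol Summary and the two-consecutive-misses rule in 5.5. Windows: month 1, days 28-35; month 3, 90 ± 7 = days 83-97; month 6, 180 ± 14 = days 166-194; month 12, 365 ± 28 = days 337-393.

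| Contacts missed | Second window closes | Scheduled contacts still ahead |
|---|---|---|
| 1 and 3 months | day 97 | 6 months, 12 months |
| 3 and 6 months | day 194 | 12 months |
| 6 and 12 months | day 393 | none |

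These are approximate starting points for closure. The letter follows failed calls, so closure may come later.

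**2. Which pattern reaches the primary analysis.** The primary population is the 1-month clear population (Protocol 9.2, SAP 1.4), and that status is assessed at the 1-month visit (Protocol 6.4). A subject who misses months 1 and 3 should rarely enter it. That pattern mainly affects the secondary endpoints, which SAP 2.2.3 also analyses in all registered subjects. For the primary endpoint the relevant pattern is months 3 and 6, where one scheduled contact is left.

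**3. Precision.** The SAP's figure of about 800 trial-arm subjects (against about 1,400 controls) cannot be reproduced, because the assumed rates, power and attrition are redacted. For scale only, assume equal NACE rates p in both arms and ignore stratification:

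power = Φ(0.04 / √[p(1 − p)(1/n + 1/1400)] − 1.645)

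At p = 10% and n = 800: √(0.09 × 0.0019643) = 0.01330; 0.04/0.01330 = 3.008; Φ(1.364) = 91.4%. If 5% of the 800 (40 subjects) lack an outcome, n = 760.

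| Assumed p | n = 800 | n = 760 |
|---|---|---|
| 5% | 99.4% | 99.2% |
| 8% | 95.4% | 94.8% |
| 10% | 91.4% | 90.6% |
| 12% | 87.1% | 86.2% |
| 15% | 81.1% | 80.0% |

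The loss of power is about 1 point at most.

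**4. Possible bias.** Let f be the share closed early, 10% the assumed NACE rate in retained subjects, and k × 10% the rate in closed subjects. The true rate is (1 − f) × 10% + f × k × 10% and the observed rate is 10%, so

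understatement = f × (k − 1) × 10 percentage points.

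| f | Subjects of 800 | k = 2 | k = 3 |
|---|---|---|---|
| 1% | 8 | 0.1 | 0.2 |
| 3% | 24 | 0.3 | 0.6 |
| 5% | 40 | 0.5 | 1.0 |

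If k = 1 there is no bias and the cost is precision only. The shares f, the 10% rate and k are all assumptions. The table also takes every closed subject as recoverable, so it gives upper bounds under those assumptions.

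**The case against.** The strongest reply is that no passage says contacts stop. Section 5.10 governs a form, and the one sentence in 5.5 that ends follow-up is worded for withdrawn subjects. That stands: a reader might infer that later contacts are forbidden or cancelled, and the documents do not say so. They do class loss as discontinuation, require the completion form, and mention return only for non-consecutive misses. Closure is therefore the natural reading, and sites may act on it differently.

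Other tempting readings also go too far:

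- **Two misses alone do not make a subject lost.** Attempts must fail at each time point, which means at least four calls and two letters over two windows. This limits the number affected. It does not show that the subject would also be unreachable at month 12.
- **Section 6.4 is not a firm contradiction.** Its commitment to 12 months is qualified as applying regardless of eligibility to stop the P2Y12 inhibitor, so it can be read as addressing subjects who are not 1-month clear. Read more broadly, it would require the later contacts, and 5.5 and 5.10 should then say so.
- **The effect cannot be said to fall on the trial arm alone.** The control study's follow-up rules are not in these documents.

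The planned outcome imputation in SAP 2.9 also counts in the plan's favour, but it is a sensitivity analysis and does not replace a status that a contact could have obtained. Finally, the unredacted text does not state when the primary analysis is run (SAP 2.4 lists 6- and 12-month windows). If it is run before the 12-month contacts, they cannot help it, although they would still serve the 6-12 and 1-12 month endpoints.

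**Conclusion.** The point holds as a gap in the follow-up rules. Followed as written, they lead most naturally to closing a subject who misses months 3 and 6 from about day 194, with one scheduled contact unused and no stated way back. The effect on power is negligible. The possible bias is at most 0.1-1.0 points against the 4.0-point margin, for 1-5% closed early at 2-3 times an assumed 10% NACE rate. The actual effect would be smaller, because only some of these subjects would be reached, and for the primary analysis only information that arrives before it is run counts. A reader might conclude that the primary result is compromised; without a loss rate, and with the exposure confined largely to one pattern of missed visits, the documents do not support that. This is an improvement worth making because it is cheap.

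**What to change.** In 5.5, state that after two consecutive misses, contact is still attempted at every remaining scheduled time point, at least for vital status and endpoint events; that a subject reached later resumes follow-up; and that events dated 1-6 months learned in this way count in the primary endpoint.

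In 5.10, make loss to follow-up final only after the 12-month window closes (day 393). If the sponsor and ethics committee need earlier notice, keep the form at its present time but make it reversible.

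The cost is a few sentences of protocol text, one or two more contact attempts for few subjects, and a loss-to-follow-up count that is final only at month 12.

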6.0 TREATMENT AND EVALUATION**6.1 Baseline and Pre-procedure****6.1.1 Laboratory Assessments**

Baseline 12-lead electrocardiogram (ECG) and laboratory assessments (such as blood counts, chemistry panel and lipid panel, cardiac enzymes, etc) should be obtained per site's standard care. Baseline laboratory results related to inclusion/exclusion criteria should be available and reviewed prior to the index procedure for screening.

6.1.2 Clinical Assessments

Subject demographics (age, gender, race), height, weight, family history of coronary artery disease (CAD), smoking status, cardiac history (myocardial infarction, diabetes mellitus, hypertension, hypercholesterolemia, and previous PCI/CABG information), subject's current cardiac status (presentation of CAD and multivessel disease) and indication of high bleeding risk (per criteria specified in **Section 5.3.1.1**) will be obtained and recorded in electronic case report form (eCRF).

6.1.3 Pre-procedure Antiplatelet Medication

Subjects must receive a loading dose of aspirin and/or a P2Y12 inhibitor (Clopidogrel, Prasugrel or Ticagrelor). The dosages of aspirin and P2Y12 inhibitor shall be determined by physician per standard of care and label indication for loading dose usage. The choice of P2Y12 inhibitor is per site standard of care, but clopidogrel is strongly recommended for HBR subjects. The loading of P2Y12 inhibitor can be omitted only if the subject is on chronic usage (≥ 7 days). Subjects that are not on chronic usage must be loaded with P2Y12 inhibitor. It is recommended that the subject be loaded with aspirin, even if the subject is on chronic usage of aspirin (≥ 7 days).

[REDACTED]

**PROTOCOL ABT-CIP-10398 XIENCE 28 Global Study**

The details of the antiplatelet loading dose, including type of drug, dosage, date and time, will be recorded in eCRF. In addition, whether the subject is taking oral anticoagulants will also be collected.

6.2 Index Procedure

Only XIENCE stent can be used for target lesion(s). Stent implantation procedure should be performed according to the instruction for use (IFU) of the XIENCE family stent used. If XIENCE stent is delivered beyond the guide catheter but not implanted, the subject cannot be registered in the trial. If other DES was implanted, the subject cannot be registered in the trial.

In this trial, a maximum of three target lesions may be treated with a maximum of two target lesions per epicardial vessel. Non-target lesion (i.e., lesions that do not meet the angiographic eligibility criteria) treatments are not allowed during the index procedure.

Subjects may receive appropriate anticoagulation and other therapy according to standard hospital practice.

Overlapping stents are not allowed in the trial, whether planned or for bailout. Subjects who received overlapping stents cannot be registered in this trial.

Bifurcation lesions are allowed in this trial. However, subjects who received double stenting for bifurcation lesions cannot be registered in this trial.

Lesion characteristics (lesion location, % diameter stenosis, TIMI flow, RVD, lesion length, thrombus presence, bifurcation or not, lesion complexity), device (device name, size, number of device implanted, bailout usage, overlapping stent) and procedural information (procedure time, access site, procedural anticoagulant and anti-thrombotic medications, any procedure complications) will be collected and recorded in eCRF.

6.3 Post-procedure

6.3.1 Post-procedure Laboratory and Clinical Tests

Post-procedure ECG and cardiac enzymes are not mandatory in the trial, and shall be performed per site's standard care. CK and CK-MB are preferred. If CK and CK-MB are not available, troponin should be collected.

6.3.2 Antiplatelet Medications during Follow-up

- All subjects must receive ≥ 75 to ≤ 100 mg of aspirin daily throughout the trial. All subjects must maintain a minimum of 75 mg of clopidogrel daily or 5 or 10 mg of prasugrel daily (10 mg preferred in most subjects*) or 90 mg twice daily of ticagrelor for 1 month (as short as 28 days) following the procedure.
 - The choice of P2Y12 inhibitor is per site standard of care, but clopidogrel is strongly recommended for HBR subjects.
 - For subjects taking chronic anticoagulants, dual therapy (oral anticoagulant and a P2Y12 inhibitor, clopidogrel preferred) may be considered within the first month per investigator's discretion.
- At 1-month follow up, subject will be assessed for their eligibility of P2Y12 inhibitor discontinuation. Eligible subjects will discontinue P2Y12 inhibitor as early as 28 days and receive ≥ 75 to ≤ 100 mg of aspirin daily through 1-year follow-up during the trial if they are "1-month clear", defined as subjects who are free from myocardial infarction

**PROTOCOL ABT-CIP-10398 XIENCE 28 Global Study**

(modified ARC), repeat coronary revascularization, stroke, or stent thrombosis (ARC definite/probable) within 1 month (prior to 1-month visit but at least 28 days) after stenting AND have been compliant with 1-month dual antiplatelet therapy (DAPT) without interruption of either aspirin and/or P2Y12 receptor inhibitor for > 7 consecutive days. Subjects who were on dual therapy during the first month (anticoagulant and a P2Y12 inhibitor) will discontinue the P2Y12 inhibitor after 1 month and if they are assessed as “1-month clear”. These subjects will start aspirin such that they will be on aspirin and anticoagulant for the remainder of the trial.

If a subject was event-free and DAPT compliant (as defined above) during the first month, but does not stop P2Y12 inhibitor after the 1-month visit, due to physician’s or subject’s decision, this subject will be considered as “1-month not clear”.

[REDACTED]

- Subjects who are not “1-month clear” are NOT eligible for P2Y12 inhibitor discontinuation. These subjects will be treated per the investigator's discretion and will continue to be followed up through 12 months.

*For prasugrel subjects < 60 kg in weight or ≥ 75 years of age, a maintenance dose of 5 mg per day is allowable.

The use of the above antiplatelet medications, including the start and stop date, any changes, as well as the reason to stop, will be documented in the eCRF.

6.3.3 Other Chronic Concomitant Medications

Administration of concomitant medications other than any approved P2Y12 inhibitors and aspirin are not required in this protocol. Subjects may receive other medications as needed per physician’s discretion.

6.4 Clinical Follow-up for All Subjects

Subjects registered in the trial will receive the following clinical follow-up:

- 1 month (28-35 days): office visit (Note: for subjects who have difficulty scheduling an office visit due to special circumstances, 1-month follow-up may be performed via telephone per physician’s discretion.)
- 3 months (90 \pm 7 days): office visit/telephone contact (office visit is strongly recommended whenever possible)
- 6 months (180 \pm 14 days): office visit/telephone contact (office visit is strongly recommended whenever possible)
- 12 months (365 \pm 28 days): office visit/telephone contact (office visit is strongly recommended whenever possible)

[REDACTED]

**PROTOCOL ABT-CIP-10398 XIENCE 28 Global Study**

Clinical follow-up visits should be conducted by the investigator or trial personnel who have been trained to the protocol. At 1-month follow-up visit, the investigator or designee will assess whether the subject is “1-month clear” and eligible for P2Y12 inhibitor discontinuation per criteria defined in **Section 6.3.2**.

All registered subjects will be followed up through 12 months, regardless of eligibility to discontinue P2Y12 inhibitor.

The following information will be collected at each of the time points:

- Any adverse events
- Use and compliance of protocol required antiplatelet medication
- Details of any subsequent coronary interventions (e.g., repeat PCI or CABG).

Note that information obtained through indirect contacts with a subject’s healthcare provider or immediate family member will NOT be considered as a trial visit.

6.5 Additional Follow-up Visits for All Subjects

Additional subject visits, such as unscheduled visits, may occur as clinically warranted. The following information will be collected and recorded in eCRF:

- Any adverse events
- Use and compliance of protocol required antiplatelet medication
- Details of any subsequent coronary interventions (e.g., repeat PCI or CABG).

If an unscheduled visit is conducted due to a suspected ischemic cardiac event, cardiac enzymes and ECG may be performed per site’s standard care. CK and CK-MB are preferred. If CK and CK-MB are not available, troponin should be collected.

All efforts must be made to obtain follow-up information on subjects who have undergone procedures or have been treated for adverse events in a non-trial-related hospital(s).

